**A Multicenter Randomized Controlled Clinical Study on the
Application of a Novel Expandable OLIF Cage with Posterior Bone
Grafting**

Date: 2025.04.21

This project aims to systematically evaluate the safety, efficacy, and clinical value of the novel expandable OLIF cage through a prospective, multicenter, randomized controlled trial, providing scientific evidence for the advancement of spinal surgical techniques. Specific components include:

1. Study Population:

Inclusion criteria: (1) Age between 40 and 80 years; (2) Diagnosed with lumbar disc degeneration, lumbar spinal stenosis (Grade A–C), degenerative spondylolisthesis (Grade I–II), or isthmic spondylolysis with or without spondylolisthesis (Grade I–II); (3) Single-level lumbar disease located at L2/3, L3/4, or L4/5; (4) Completed all necessary assessments and scheduled for OLIF surgery under general anesthesia; (5) Willing and able to comply with the study protocol; (6) Provided written informed consent prior to registration and fully understands their right to withdraw at any time without penalty.

Exclusion criteria: (1) Bony central canal or lateral recess stenosis, or non-contained disc herniation requiring direct decompression; (2) Previous lumbar posterior or retroperitoneal surgery, or abnormal iliac vascular sheath-psoas interval; (3) Severe spinal deformity or osteoporosis (T-score < -3.0); (4) Severe cardiac dysfunction (LVEF < 30% or NYHA Class IV), severe hepatic dysfunction (Child-Pugh Class C), severe renal dysfunction (on dialysis), or ASA Class IV or above; (5) Recurrent severe infections or other serious comorbidities; (6) Conditions requiring simultaneous surgeries; (7) Participation in other clinical trials; (8) Inability to comply with follow-up requirements.

2. Surgical Protocol and Procedure Standardization:

The novel expandable OLIF cage with posterior bone grafting will be used. Intraoperatively, height expansion technology will restore intervertebral height and lumbar lordosis, while posterior grafting promotes interbody fusion. All procedures will follow standard surgical protocols and be performed by trained spine surgeons to ensure consistency.

3. Evaluation Indicators:

Perioperative data will be recorded, including operative time, intraoperative blood loss, time to ambulation, length of hospital stay, and complications. Clinical outcomes will be assessed using the Visual Analogue Scale (VAS) and Oswestry Disability Index (ODI). Imaging assessments will include intervertebral height, coronal and sagittal Cobb angles, and evaluation of interbody fusion.

4. Data Collection and Analysis:

An electronic medical record system and follow-up platform will be used to establish a multi-dimensional data collection framework:

- **Preoperative baseline data:** Demographics (age, sex, BMI), disease duration, comorbidities, radiological parameters (intervertebral height, lumbar curvature);
- **Intraoperative data:** Operative time, blood loss, graft volume, number of fluoroscopy exposures, neuro-monitoring data;
- **Postoperative follow-up data:**
 - **Imaging (Immediate/6M/12M):** Bridwell grading for fusion, intervertebral height restoration rate, cage subsidence;
 - **Clinical (Pre/3M/6M/12M):** VAS (back/leg), ODI, SF-36 quality of life scale;
 - **Complications:** Categorized records of neurological injury, adjacent segment degeneration, instrumentation-related complications;
 - **Dynamic monitoring:** Scheduled follow-up at 1, 3, 6, and 12 months with electronic follow-up records.

Efforts will be made to ensure data integrity and accuracy. Statistical analysis will compare clinical parameters across groups to evaluate the superiority of the novel cage.

5. Sample Size Calculation:

The baseline incidence of cage subsidence after OLIF surgery is approximately 30%. The expected reduction to 15% with the novel expandable OLIF cage was used in the calculation. With a two-sided alpha of 0.05 and power of 90%, the total sample size is estimated to be approximately 340 participants. There will be 7 centers, each expected to enroll 45–50 patients.

6. Randomization Method:

Eligible participants will be randomized using PASS 11.0 software. Once written informed consent is obtained and baseline assessments are completed, eligible patients will be randomized in sequence according to the pre-generated randomization list.

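### Does leaving the T-score off the preoperative list in Section 4 cost the subsidence comparison a usable baseline covariate?

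*Protocol*

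**What the plan says.** Four places in the protocol bear on this.

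- Section 1, exclusion criterion 3, rules out "Severe spinal deformity or osteoporosis (T-score < -3.0"). Bone density therefore has to be known or judged at screening, and patients at or above the cut-off can still differ in it.
- Section 4, preoperative line, lists "Demographics (age, sex, BMI), disease duration, comorbidities, radiological parameters (intervertebral height, lumbar curvature"). Neither T-score nor bone mineral density is named there or anywhere else as a recorded variable. The same section says the data are assembled from an electronic medical record system and a follow-up platform.
- Section 5 sizes the trial on subsidence: "The baseline incidence of cage subsidence after OLIF surgery is approximately 30" per cent, and "The expected reduction to 15% with the novel expandable OLIF cage was used in the calculation". Section 4 collects that outcome under postoperative imaging, as "Bridwell grading for fusion, intervertebral height restoration rate, cage subsidence".
- Section 6 puts baseline work before allocation: "Once written informed consent is obtained and baseline assessments are completed, eligible patients will be randomized in sequence".

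**The concern.** Read together, these places suggest a gap. The protocol treats bone density as important enough to exclude on, sizes the trial on an outcome that bone density might plausibly predict, and takes baseline measurements before randomization, which is what a legitimate covariate requires. Yet the one line that lists preoperative data leaves the value out. If seven centers recorded only the listed items, no analysis plan could tabulate T-score by arm or adjust for it without returning to source records.

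Bias would not be at stake, because randomization protects the unadjusted comparison. What could be lost is some precision and a check on chance imbalance.

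**Working it through.** **1. The sample size.** Inputs from Section 5: 30% versus 15%, two-sided alpha 0.05, power 90%. Allocation of 1:1 is assumed, as no ratio is stated.

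Pooled formula: n per arm = [1.960·√(2·0.225·0.775) + 1.282·√(0.30·0.70 + 0.15·0.85)]² / 0.15² = 161 after rounding up, or 322 in total.

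With continuity correction it is 174 per arm, 348 in total. The stated figure of about 340 is within 3% of that ((348 − 340)/348 = 2.3%). It also equals 322/0.95 = 339 if 5% dropout is assumed. At 170 per arm the pooled formula gives 91.5% power. The figure reproduces, and no covariate enters it.

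**2. Is the preoperative line a complete list?** Compare it with the rest of the protocol:

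| Item | Collected or needed before surgery | Named in the preoperative line |
|---|---|---|
| VAS, ODI, SF-36 | Yes; the Clinical line of Section 4 has a preoperative time point | No |
| Coronal and sagittal Cobb angles | Imaging measures in Section 3 | Only loosely, as lumbar curvature |
| LVEF, NYHA, Child-Pugh, ASA | Needed for exclusion criterion 4 | No |
| Stenosis and slip grade, operated level | Needed for inclusion criteria 2 and 3 | No |
| T-score | Needed for exclusion criterion 3 | No |

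The first row settles it: three instruments are certainly collected before surgery and are missing from the line. Absence from it is therefore weak evidence that a value goes unrecorded, and T-score is treated like every other eligibility measurement.

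**3. Must the value be on that list to be used?** No. A baseline covariate has to be measured before randomization; it may be abstracted later. If some values were missing, little would change. In simulation at 322 patients, with 10% missing at random and mean-imputed, the power of adjusted logistic regression falls by at most 0.3 points (0.947 to 0.944, at an odds ratio of 3.0 per SD).

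**4. How much precision is in play?** The protocol gives no association between T-score and subsidence, so the odds ratio per SD is assumed. Let p0 and p1 be the individual risks in the two arms under a logistic model with a standard normal T-score and marginal risks of 30% and 15%. Variances are multiplied by N:

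- Unadjusted: 2·(0.21 + 0.1275) = 0.675
- Adjusted (standardized risk difference): 2·(E[p0(1 − p0)] + E[p1(1 − p1)]) + Var(p1 − p0)
- Power at 340: Φ(0.15/√(variance/340) − 1.96)

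Unadjusted: 0.15/√(0.675/340) = 3.37, so power is Φ(1.41) = 0.920. At an odds ratio of 2.0: 0.928 × 0.675 = 0.626; 0.15/√(0.626/340) = 3.49; power is 0.938.

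| Assumed odds ratio per SD | Variance ratio | Power at 340 | Gain (points) | Equivalent patients, 340·(1 − ratio) |
|---|---|---|---|---|
| 1.25 | 0.992 | 0.922 | 0.2 | 3 |
| 1.5 | 0.973 | 0.927 | 0.7 | 9 |
| 2.0 | 0.928 | 0.938 | 1.8 | 25 |
| 2.5 | 0.883 | 0.948 | 2.8 | 40 |
| 3.0 | 0.844 | 0.956 | 3.6 | 53 |

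Simulation at 340 (10,000 runs per scenario) gives gains of 0.6, 1.7, 2.5 and 3.1 points for odds ratios of 1.5 to 3.0. At 322 with no association, adjustment costs about 0.3 points.

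**5. Chance imbalance.** The standard error of the between-arm difference in SD units is 2/√340 = 0.108, so a difference of 0.2 SD or more, in either direction, has probability 0.065. At an odds ratio of 2.0 it would move the log odds by 0.2·ln 2 = 0.139. The planned log odds ratio is ln(0.30/0.70) − ln(0.15/0.85) = 0.887, and 0.139/0.887 is about 16%. This sets a conditional shift against a marginal effect, so it is only indicative. The unadjusted test already allows for such imbalance in its error rate.

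**The case for a change.** The best case for raising the point is that an analysis plan can choose a model but cannot create data. What centers record is settled by the data-collection section. A comorbidity entry of osteoporosis, yes or no, would lose the numeric value. Naming the T-score would cost almost nothing where it is already measured for eligibility, and prospective capture in one format is tidier than abstraction from seven centers.

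Much of this stands as good practice. The T-score is not named, the arithmetic is sound, and writing the field down would do no harm. What does not stand is the step from an unnamed field to lost information. It requires that centers record only what the line lists, and the protocol's own preoperative VAS, ODI and SF-36 contradict that reading. What remains is possible abstraction work. That a T-score sits in each patient's record is an inference, since the protocol does not say that every patient has a bone-density scan; but where none was done, a field on the list would not supply the value by itself.

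The gain is also less certain than it looks. It is measured against no adjustment at all, not against adjustment for age, sex and BMI, which are already collected and may carry part of the same information. The exclusion cut-off may also narrow the spread of T-scores among enrolled patients.

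**Conclusion.** The concern does not hold. The protocol makes no wrong statement here and does not contradict itself, and the analysis it implies remains valid without the T-score. The preoperative line is a summary, and its silence on one eligibility value does not show that the value is lost. Whether to adjust for T-score or report it by arm can be left to the statistical analysis plan, which is not at hand.

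The most that could be at issue is a precision gain at 340 patients of about 0.2 points of power at an odds ratio of 1.25 per SD, 1.8 points at 2.0 and 3.6 points at 3.0, on an unadjusted power of about 92%. These figures assume 1:1 allocation, a normally distributed T-score, complete data and an association that the protocol does not give. A sponsor may choose to name the field, but the protocol does not need correcting for it.

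### Does leaving the Cobb angles off the Section 4 imaging list mean that restoration of lordosis cannot be assessed?

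*Protocol*

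**What the plan says.** Protocol, Section 3, sets the imaging outcomes: "Imaging assessments will include intervertebral height, coronal and sagittal Cobb angles, and evaluation of interbody fusion". It gives no time points. It also lists the perioperative measures (including time to ambulation and hospital stay), complications, VAS and ODI.

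Protocol, Section 4, is the only schedule. Its baseline list covers intervertebral height and lumbar curvature. Its post-operative imaging row, for the immediate, 6-month and 12-month films, reads "Bridwell grading for fusion, intervertebral height restoration rate, cage subsidence". VAS, ODI and SF-36 are taken before surgery and at 3, 6 and 12 months. Complications have a row of their own with no dates. The visit plan is "Scheduled follow-up at 1, 3, 6, and 12 months with electronic follow-up records".

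Protocol, Section 2, describes the surgical technique and says that "height expansion technology will restore intervertebral height and lumbar lordosis".

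Protocol, Section 5, bases the sample size on cage subsidence: about 30% at baseline incidence, and for the new cage "The expected reduction to 15% with the novel expandable OLIF cage was used in the calculation".

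**The concern.** Section 2 attributes two mechanical effects to the cage: restored disc height and restored lordosis. Height has both a baseline and a follow-up entry in Section 4. Alignment has a baseline entry for curvature and nothing afterwards. If the case report form were built from Section 4 alone, the difference between arms in sagittal or coronal alignment could not be estimated, although Section 3 lists both angles as outcomes.

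Other differences between the sections suggest that the lists were not compared. Time to ambulation and hospital stay have no row in Section 4. Subsidence and SF-36 are in Section 4 but not in Section 3. The 1-month visit has neither clinical scores nor imaging. Fusion grading shares a row that includes the immediate film, when fusion cannot yet have occurred. With seven centres, two lists that differ could lead to uneven data capture.

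**Working it through.** **Step 1. Which outcome carries the trial.** Inputs from Section 5: p1 = 0.30, p2 = 0.15, two-sided alpha 0.05, power 90%, total about 340. A 1:1 allocation is assumed, as the ratio is not stated.

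n per arm = [z(0.975)·√(2·p̄·(1−p̄)) + z(0.90)·√(p1(1−p1) + p2(1−p2))]² / (p1−p2)², with p̄ = 0.225

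= [1.960·√0.34875 + 1.2816·√0.3375]² / 0.0225 = (1.1575 + 0.7445)² / 0.0225 ≈ 160.8, so 161 per arm and 322 in total.

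With a continuity correction the result is 174 per arm, 348 in total. The stated 340 lies between the two: 348 exceeds it by 8/340 = 2.4%, and 322/0.95 = 339 if 5% dropout is assumed. The figure is reproduced, and it rests wholly on subsidence. No Cobb angle enters it.

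**Step 2. The 11 Section 3 indicators against Section 4.**

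| Section 3 indicator | Entry in Section 4 | Data lost if both sections are followed? |
|---|---|---|
| Operative time | Intraoperative list | No |
| Blood loss | Intraoperative list | No |
| Time to ambulation | None | No: Section 3 itself says it will be recorded, and it is recorded once |
| Hospital stay | None | No: same reason |
| Complications | Own row, undated | No |
| VAS | Pre, 3, 6, 12 months | No |
| ODI | Pre, 3, 6, 12 months | No |
| Intervertebral height | Baseline; restoration rate at immediate, 6, 12 months | No |
| Fusion | Bridwell grade in the imaging row | No |
| Sagittal Cobb angle | Baseline curvature only | Time point unwritten |
| Coronal Cobb angle | None | Time point unwritten |

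On a literal match, 4 of 11 indicators lack an entry after baseline. Two of those four are single perioperative facts that need no visit schedule and are already committed to in Section 3. That leaves 4 − 2 = 2 of 11.

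**Step 3. The reverse direction.** Subsidence and SF-36 are in Section 4 only. Both are therefore scheduled, so nothing is lost in collection.

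**Step 4. The 1-month visit.** Complications carry no date restriction and can be recorded then. A visit without a questionnaire or a film is not an error.

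**Step 5. The immediate film.** One time label heads three measures. The immediate film is the natural reference for height and subsidence. The text does not say that each measure is scored at each time.

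**Step 6. Can both sections be followed together?** Section 3 says what is measured; Section 4 says when films are taken and names three readings. Nothing in Section 4 excludes a further reading. Taking the angles at the immediate, 6-month and 12-month imaging times satisfies both. Even without a coronal baseline, randomised arms can be compared on the post-operative angle.

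**The case for a change.** The best case for a change is that what is measured, and when, belongs in the protocol rather than the SAP. Section 4 is the only schedule, data capture is usually built from a schedule, and an unlisted measurement can be forgotten. Re-reading stored films would rescue the angles only if the right views were taken. The protocol names no views, and a coronal angle cannot be read from a lateral film. A line added before data capture is built costs almost nothing.

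Part of this stands. The angles have no written follow-up time, and later recovery from archived films is not certain. But the loss requires a team to ignore a commitment stated in the section immediately before the schedule. The text gives no sign that centres would work from different sections; Section 4 describes an electronic record system and follow-up platform for the study. Lordosis appears in Section 2 as a description of the technique, not as a hypothesis, so no stated test depends on it. What remains is a useful drafting remark about two measures that do not drive the sample size.

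**Conclusion.** No change to the plan is needed. Two of the 11 Section 3 indicators, the sagittal and coronal Cobb angles, lack a written post-operative time point. The protocol already commits to measuring them and already schedules imaging immediately after surgery and at 6 and 12 months, so analysts and sites can fill the gap in an obvious way. It would be too strong to say that restoration of lordosis cannot be assessed. The subsidence comparison, its sample size and its collection times are unaffected.

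This rests on two assumptions that the protocol does not confirm: that the planned films include views showing both planes, and that the case report form is built from Sections 3 and 4 together. If either failed, the cost would fall on the alignment results and not on the outcome that sizes the trial.

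### The trial is sized on cage subsidence alone, but no endpoint is named primary and superiority is to be judged on unranked clinical parameters

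*Protocol*

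**What the plan says.** Four places in the protocol bear on this point.

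- **Section 5 (Sample Size Calculation)** takes a control rate of about 30% for cage subsidence and continues: "The expected reduction to 15% with the novel expandable OLIF cage was used in the calculation". Then: "With a two-sided alpha of 0.05 and power of 90%, the total sample size is estimated to be approximately 340 participants". No other outcome enters the calculation.
- **Section 3 (Evaluation Indicators)** lists perioperative data, VAS and ODI, and says of imaging: "Imaging assessments will include intervertebral height, coronal and sagittal Cobb angles, and evaluation of interbody fusion". Subsidence is not named.
- **Section 4 (Data Collection and Analysis)** has an imaging line, at the immediate, 6-month and 12-month films, with "Bridwell grading for fusion, intervertebral height restoration rate, cage subsidence". A separate line, labelled clinical, has "VAS (back/leg), ODI, SF-36 quality of life scale".
- **Section 4, closing sentence**: "Statistical analysis will compare clinical parameters across groups to evaluate the superiority of the novel cage".

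No endpoint is designated primary or secondary anywhere in the document.

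**The concern.** A two-sided alpha of 0.05 and a power of 90% are properties of one specified test. Here the specified test is the subsidence comparison in Section 5, while the sentence that says how superiority will be judged points elsewhere.

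That sentence can be read in two ways. Read narrowly, clinical parameters are the measures Section 4 itself labels clinical, and the sized outcome is left out. Read broadly, they are everything compared between the groups, and subsidence is one unranked item in a long list. Neither reading ties superiority to the outcome for which the trial was sized.

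At stake is what the trial may conclude. As worded, nothing in the protocol prevents a superiority conclusion from VAS, ODI or SF-36 when subsidence shows no benefit, and the stated error rate and power do not cover that conclusion.

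**Working it through.** **1. Does the stated sample size belong to subsidence?**

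Inputs from Section 5: p1 = 0.30, p2 = 0.15, two-sided alpha 0.05 (z = 1.960), power 90% (z = 1.282). The allocation ratio is not stated; 1:1 is assumed. Mean rate 0.225.

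Pooled-variance formula:

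n per arm = [1.960·√(2·0.225·0.775) + 1.282·√(0.30·0.70 + 0.15·0.85)]² / 0.15²
= [1.157 + 0.745]² / 0.0225 ≈ 160.8, so 161 per arm, **322 in total**.

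With continuity correction the result is 174 per arm, **348 in total**. The uncorrected 322 with an assumed 5% dropout is 322/0.95 = **339**. The stated figure of about 340 is thus consistent with its own inputs, and the arithmetic is not at fault.

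Power with 170 per arm and no dropout:

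Φ{[0.15·√170 − 1.157] / 0.581} = Φ(1.374) = **91.5%**.

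Section 5 expects 45 to 50 patients from each of 7 centres, that is 7 × 45 = 315 to 7 × 50 = 350. Over that range the power is 89.4% to 92.3%.

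**2. What would the superiority sentence allow?**

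The protocol states no decision rule, so this is an illustration. Suppose there is no true effect, each measure is tested once at two-sided 0.05, and any one significant result supports the claim. With k independent tests the chance of at least one false positive is 1 − 0.95^k in either direction, and 1 − 0.975^k if only results favouring the novel cage count. The values at correlation 0.5 assume equally correlated normal test statistics.

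| Reading | k | Either direction, independent | Either direction, correlation 0.5 | Favouring new cage, independent | Favouring new cage, correlation 0.5 |
|---|---|---|---|---|---|
| Single test | 1 | 5% | – | 2.5% | – |
| Narrow: VAS back, VAS leg, ODI, SF-36 | 4 | 18.5% | 15.6% | 9.6% | 7.8% |
| Broad: the indicators in Section 3 | 11 | 43.1% | 30.4% | 24.3% | 15.2% |

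The 11 indicators are five perioperative items (operative time, blood loss, time to ambulation, hospital stay, complications), VAS, ODI, intervertebral height, two Cobb angles and fusion. For k = 4 the either-direction figure is 17.4% at correlation 0.3 and 13.0% at 0.7.

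**3. What is the power for the other measures?**

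It cannot be derived, because the protocol gives no effect size or standard deviation for VAS, ODI, SF-36 or fusion. As a guide for a continuous measure, 170 per arm gives 90% power at a standardized difference of (1.960 + 1.282)·√(2/170) = 0.35. Power is 79% at 0.30 and 45% at 0.20.

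**4. Does the sample size survive naming subsidence?**

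Yes, if the 30% control rate fits the definition and time chosen. The protocol attaches neither to that rate. If the control rate were lower and the halving were kept (assumed scenarios), power with 170 per arm would be 84.3% at 25% against 12.5%, and 73.5% at 20% against 10%.

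**The case against.** The strongest reply is that the link is incomplete rather than absent. Sizing a trial on one outcome normally signals the primary endpoint, no other outcome is given an effect size, and Section 4 does collect subsidence on scheduled films. The intended primary can be inferred. This is fair about intent, but an inference from Section 5 does not correct the sentence in Section 4, which says what superiority rests on, and it leaves the decision time open among three films.

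The narrow reading is also said to lean on one word, since the closing phrase may be generic and would otherwise exclude fusion and disc height as well. That is plausible. It leads to the broad reading, under which subsidence is still unranked.

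Section 3 is open-ended: its reference to complications, and Section 4's category of instrumentation-related complications, might be taken to include subsidence. Other items, such as SF-36, also appear only in Section 4. The omission alone would therefore be minor. Neither heading names or ranks subsidence, however.

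The error rates assume a rule that any single result at 0.05 suffices, which the protocol does not state, and the multiplicity method may sit in an SAP that is not shown. This stands, so the rates are illustrations and not measured errors. The count of 11 is also imperfect for the broad reading, because it leaves out subsidence and SF-36 and counts VAS once. Adding subsidence and SF-36 and splitting VAS gives 14, and 1 − 0.95^14 = 51%, so 11 understates that case.

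**Conclusion.** The concern holds and should be fixed before the trial's results are known. It rests on the text alone: one outcome was sized, none is designated primary, and the superiority sentence is not tied to the sized outcome. Which endpoint carries the conclusion belongs in the protocol, whatever an SAP may add on multiplicity.

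The gap runs from a single subsidence test at 5% with 91.5% power to an unranked set whose false-positive chance, on the narrow reading, is about 16% to 18.5% in either direction, or about 8% to 9.6% favouring the novel cage. These figures assume 1:1 allocation, no dropout, one test per measure and correlations between 0 and 0.5. The finding itself needs none of these assumptions.

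**What to change.** Amend the protocol in three places.

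1. **Section 3:** add cage subsidence as the single primary endpoint, with its definition and one decision time chosen by the sponsor from the scheduled films.
2. **Section 4:** replace the superiority sentence with one to this effect: *superiority will be concluded from the between-group comparison of the primary endpoint, cage subsidence, at two-sided 0.05; all other parameters are secondary*. The testing of secondary parameters can be left to the SAP.
3. **Section 5:** confirm that the 30% planning rate applies to the chosen definition and time.

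The cost is a short amendment once the sponsor has made that choice and check. No new data are needed, because subsidence is already collected, and about 340 patients stands if the 30% rate fits. If the rate proves lower, the sample size must be revisited. The sponsor gives up the option of claiming superiority on other parameters alone. If another endpoint is meant to carry the claim, the trial must be re-sized on that endpoint.

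### Does the target of about 340 participants fall short of the stated 90% power once lost follow-up and the 45–50 per centre plan are considered?

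*Protocol*

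**What the plan says.** Protocol section 5 (Sample Size Calculation) gives a control subsidence rate of about 30% and adds: "The expected reduction to 15% with the novel expandable OLIF cage was used in the calculation". It continues: "With a two-sided alpha of 0.05 and power of 90%, the total sample size is estimated to be approximately 340 participants". The recruitment plan comes next: "There will be 7 centers, each expected to enroll 45–50 patients".

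Section 4 (Data Collection and Analysis) lists when subsidence is read: "Imaging (Immediate/6M/12M): Bridwell grading for fusion, intervertebral height restoration rate, cage subsidence". Section 5 does not tie the calculation to any one of these visits.

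The protocol does not state the test behind the calculation, the allocation ratio, an expected loss rate, or whether 340 counts enrolled or evaluable patients. Section 6 (Randomization Method) says only that "eligible patients will be randomized in sequence according to the pre-generated randomization list".

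**The concern.** Two features invite suspicion.

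First, the textbook chi-square formula gives 322 for these inputs, not 340, and nothing explains the gap of 18. If 340 is 322 plus an allowance, that allowance is only about 5%, which is thin for an endpoint imaged up to 12 months after surgery. If 340 comes from an exact or continuity-corrected formula, there is no allowance at all.

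Second, the centre plan runs from 315 to 350. Its midpoint, 332.5, lies below 340, and its low end lies below even the 322 needed for the chi-square test.

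If both went badly, the trial would run at lower power than the protocol claims, and a null result would be read as stronger evidence against the new cage than it is. An analysis plan written later could not restore patients who were never enrolled.

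**Working it through.** **Inputs.** From section 5: p1 = 0.30, p2 = 0.15, two-sided alpha 0.05 (z = 1.95996), power 0.90 (z = 1.28155), total about 340. Assumed: 1:1 allocation, and the loss rates used below, since the protocol gives none.

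**Reproducing the stated total.** Let d = 0.15, mean rate 0.225, 2 × 0.225 × 0.775 = 0.34875, and 0.30 × 0.70 + 0.15 × 0.85 = 0.3375.

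- Pooled chi-square: n = (1.95996 × √0.34875 + 1.28155 × √0.3375)² / 0.15² = 160.8, so 161 per arm, 322 in total.
- Unpooled: n = (1.95996 + 1.28155)² × 0.3375 / 0.15² = 157.6, so 158 per arm, 316 in total.
- Continuity-corrected: n = (160.78/4) × (1 + √(1 + 4/(160.78 × 0.15)))² = 173.9, so 174 per arm, 348 in total.
- Fisher's exact test, by full enumeration: power first reaches 90% at 172 per arm, 344 in total.
- Pooled figure with 5% loss: 322/0.95 = 339.

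So 340 is one patient from the 5% route (339), 4 below Fisher (4/344 = 1.2%) and 8 below the corrected figure (8/348 = 2.3%). The protocol presents its total as approximate, and every one of these routes is compatible with it.

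**Loss that 340 can absorb at 90% power.** Pooled: 1 − 322/340 = 5.3%. Unpooled: 1 − 316/340 = 7.1%. Under Fisher, power at 340 is already 0.3 points short, at 89.7%.

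**Power at a given evaluable total.** With n per arm, power = Φ[(0.15√n − 1.95996 × √0.34875)/√0.3375]. At n = 170 this is Φ(1.374) = 91.5%. At n = 153 (340 less 10%) it is Φ(1.201) = 88.5%.

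| Enrolled | Test | No loss | 10% loss | 20% loss |
|---|---|---|---|---|
| 340 | Pooled chi-square | 91.5% | 88.5% | 84.6% |
| 340 | Fisher | 89.7% | 86.3% | 81.4% |
| 315 | Pooled chi-square | 89.4% | 86.0% | 81.8% |
| 315 | Fisher | about 87% | 83.5% | 78.1% |
| 350 | Pooled chi-square | 92.3% | 89.4% | 85.6% |
| 350 | Fisher | 90.7% | 87.3% | 82.8% |

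**Centre plan.** 7 × 45 = 315 and 7 × 50 = 350, so the range contains 340, which needs 340/7 = 48.6 per centre. Measured against the 322 evaluable patients of the pooled test, 46 per centre is enough before loss (7 × 46 = 322). At the midpoint of 332.5, pooled power with no loss is Φ(1.337) = 90.9%.

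**Scale.** Section 5 gives the control rate only approximately. If it were 29% (an assumption) with the new cage still at 15%, then d = 0.14, mean rate 0.22, 2 × 0.22 × 0.78 = 0.3432 and 0.2059 + 0.1275 = 0.3334. At n = 170, power = Φ[(0.14√170 − 1.95996 × √0.3432)/√0.3334] = Φ(1.173) = 88.0%. One percentage point in the control rate costs 3.5 points of power (91.5 to 88.0). A 10% loss costs 3.0 (91.5 to 88.5).

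**The case for a change.** The strongest argument for a change is that low enrolment and missing films can occur together. At 315 enrolled with 10% loss, power is 86.0% (chi-square) or 83.5% (Fisher). With 20% loss it is 81.8% or 78.1%, so the type II error reaches 14% to 22% across these cases instead of the stated 10%. Enrolment totals belong in the protocol and cannot be repaired by an analysis plan. A centre plan whose midpoint is 332.5 does sit a little under its own target. Writing down the loss assumption would cost nothing.

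The figures stand, and so does the observation that section 5 is silent on loss. They do not show that the stated total is wrong. The worst cases need every centre at its minimum and substantial loss as well, and the protocol gives no basis for either. The per-centre numbers are expectations, with nothing to make them caps, so centres can recruit on to the total. Counting 12-month loss one for one against the evaluable total also assumes a 12-month endpoint and that patients with an earlier film contribute nothing; section 5 says neither. The choice of test and the handling of missing films are commonly left to the analysis plan. Finally, the remedy on offer adds no patients, so the trial would have exactly the power it has now.

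**Conclusion.** The concern does not call for a change. About 340 patients is a correct total for 30% against 15% at two-sided 0.05 and 90% power. It gives 91.5% with a chi-square test and 89.7% with Fisher's test when all are evaluable, and it absorbs 5.3% (pooled) to 7.1% (unpooled) loss before chi-square power falls below 90%. At an assumed 10% loss the chi-square shortfall is 1.5 points, less than the uncertainty in a control rate given only approximately. Under Fisher the shortfall at that loss is larger, 3.7 points.

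The centre range of 315 to 350 contains 340, so the two statements do not conflict; even 315 fully evaluable patients give 89.4% by chi-square.

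The remaining gap is descriptive: section 5 does not say whether 340 is enrolled or evaluable, or what loss it allows for. Analysts can fill this in by reporting power at the number actually evaluable. The conclusion rests on 1:1 allocation and on loss staying near or below 10%. Evidence of loss around 15% to 20% would reopen the question: chi-square power at 340 enrolled would then be 86.7% to 84.6%, and lower under Fisher. The protocol offers no such evidence.
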